#### 7.1.5.2. Incomplete Dates

All AEs with incomplete onset dates will be imputed for TEAE determination. The imputation rules are as follows:

- If the day is missing but the month and year are available, then the imputed day will be the first day of the month or the first dosing date if they have the same month and year, whichever is later.
- If the day and month are missing but year is available, then the imputed day and month will be 01 January or the first dosing date if they have the same year, whichever is later.

An AE with completely missing onset and stop dates, or with the onset date missing and a stop date later than the first dosing date of study drug, will be considered to be treatment emergent. In addition, an AE with the onset date missing and incomplete stop date with the same or later month and year (or year alone if month is not recorded) as the first dosing date of study drug will be considered treatment emergent.

#### 7.1.6. Summaries of Adverse Events and Deaths

Treatment-emergent AEs will be summarized based on the Safety Analysis Set.

##### 7.1.6.1. Summaries of AE Incidence by Severity

A brief, high-level summary of number and percentage of subjects who experienced the following TEAEs will be provided by treatment group:

- Any TEAE;
- Any grade 1 or 2 TEAE;
- Any grade 3 or 4 TEAE;
- Any TEAE related to GS-1423;
- Any grade 1 or 2 TEAE related to GS-1423;
- Any grade 3 or 4 TEAE related to GS-1423;
- Any TE SAE;
- Any grade 1 or 2 TE SAE;
- Any grade 3 or 4 TE SAE;
- Any TEAE leading to death;

- Any TE SAE related to GS-1423;
- Any TEAE leading to premature discontinuation of GS-1423;
- Any TEAE leading to temporary interruption of GS-1423;
- Any grade 1 or 2 TEAE leading to temporary interruption of GS-1423;
- Any grade 3 or 4 TEAE leading to temporary interruption of GS-1423;
- Any dose limiting toxicity

For the AE categorizes described below, the number and percentage of subjects who experienced at least 1 TEAE summaries will be provided by SOC, PT, maximum severity, and treatment group:

- TEAEs
- TE treatment related AEs

Summary tables (number and percentage of subjects) of treatment-emergent AEs (by SOC and PT) will be provided by cohort and overall as follows:

- TEAEs
- TEAEs with Grade 3 or higher
- TE treatment-related AEs
- TE Treatment-related AEs with Grade 3 or higher
- TE SAEs
- TE treatment-related SAEs
- TEAEs leading to premature discontinuation of GS-1423
- TEAEs leading to temporary interruption of GS-1423
- TEAEs leading to deaths

The above TEAEs excluding TEAEs leading to deaths will also be summarized by PT only in descending order of total frequency. Additionally, all TEAEs will be summarized by PT and severity.

Multiple events will be counted only once per subject in each summary. Adverse events will be summarized and listed first in alphabetic order of SOC and then by PT in descending order of

total frequency within each SOC. For summaries by severity, the most severe severity will be used for those AEs that occurred more than once in a given subject during the study.

In addition, data listings will be provided for the following:

- All AEs, indicating whether the event is treatment emergent and related to study drug
- All AEs with Grade 3 or higher
- All SAEs
- All AEs leading to death
- All AEs leading to premature discontinuation of study drug
- TEAEs leading to temporary interruption of study drug

#### 7.1.6.2. Summary of Deaths

A summary (number and percentage of subjects) of deaths will be provided by treatment group and overall, with the cause of the death (AE, PD, or other reasons). The summary will include the following categories:

- All deaths
- Deaths within 30 days of the last dosing of study drug
- Deaths after 30 days of the last dosing of study drug

A list of all deaths with primary cause of death will be provided.

#### 7.1.6.3. Dose Limiting Toxicity

A listing of the DLT AEs will be provided by cohort including cohort number with dose level, subject identification, actual dose amount prior to or on the start date of the AE, DLT term from the investigator as well as CTCAE term and associated severity grade, if available.

A summary of DLT will be presented by PT.

Late onset AEs meeting DLT definition occurring beyond the 28-day DLT observation period will be listed and summarized by PT as well.

## 7.2. Laboratory Evaluations

CCI

CCI

## CCI

### 7.2.2.1. Treatment-Emergent Laboratory Abnormalities

Treatment-emergent laboratory abnormalities are defined as values that increase at least 1 toxicity grade from baseline at any postbaseline time point, up to and including the date of last dose of study drug plus 30 days subjects who permanently discontinued study drug. If the relevant baseline laboratory value is missing, any abnormality of at least Grade 1 observed within the time frame specified above will be considered treatment emergent.

### 7.2.2.2. Summaries of Laboratory Abnormalities

The summaries (number and percentage of subjects) for treatment-emergent laboratory abnormalities will be provided by lab test and dose cohort; subjects will be categorized according to the most severe postbaseline abnormality grade for a given lab test:

- Graded TE laboratory abnormalities
- TE Grade 3 or 4 laboratory abnormalities

For all summaries of laboratory abnormalities, the denominator is the number of subjects with nonmissing postbaseline values up to 30 days after the last dosing date.

A by-subject listing of treatment-emergent Grade 3 or 4 laboratory abnormalities will be provided by subject ID number and visit in chronological order. This listing will include all test results that were collected throughout the study for the lab test of interest, with all applicable severity grades displayed.

### 7.3. Body Weight, Body Mass Index and Vital Signs

Descriptive statistics will be provided by dose cohort for body weight, body mass index (BMI) and vital signs as follows:

- Baseline value
- Postbaseline maximum value
- Postbaseline minimum value
- Change and percentage change from baseline to postbaseline maximum value
- Change and percentage change from baseline to postbaseline minimum value

A baseline value will be defined as the last available value collected on or prior to the date/time of first dose of study drug. Weight, BMI and each vital signs measurement (including

temperature, pulse, respiratory rate, and blood pressure) will be summarized. Change from baseline to a postbaseline visit will be defined as the postbaseline value minus the baseline value.

In the case of multiple values in an analysis window, data will be selected for analysis as described in Section 3.8.3. No formal statistical testing is planned.

A by-subject listing of vital signs will be provided by subject ID number and visit in chronological order. Body weight and BMI will be included in the vital signs listing, if space permits. If not, they will be provided separately.

## 7.4. Prior and Concomitant Medications

Medications collected at screening and during the study will be coded using the current version of the World Health Organization (WHO) Drug dictionary.

### 7.4.1. Prior Medications

Prior medications are defined as any medications taken before a subject was administered the first dose of study drug.

Prior medications will be summarized by Anatomical Therapeutic Chemical (ATC) drug class Level 2 and preferred name using the number and percentage of subjects for each dose cohort and overall. A subject reporting the same medication more than once will be counted only once within each ATC drug class when calculating the number and percentage of subjects who received that medication. [Medications may appear under multiple ATC drug classes.] The summary will be ordered alphabetically by ATC medical class and then by preferred term in order of descending overall frequency within each ATC medical class. For drugs with the same frequency, sorting will be done alphabetically.

For the purposes of analysis, any medication with a start date prior to the first dosing date of study drug will be included in the prior medication summary regardless of when the stop date is. If a partial start date is entered the medication will be considered prior unless the month and year (if day is missing) or year (if day and month are missing) of the start date are after the first dosing date. Medications with a completely missing start date will be included in the prior medication summary, unless otherwise specified.

Summaries will be based on the Safety Analysis Set. No formal statistical testing is planned.

### 7.4.2. Concomitant Medications

Concomitant medications are defined as medications taken while a subject took study drug. Use of concomitant medications will be summarized by Anatomical Therapeutic Chemical (ATC) classification Level 2 (therapeutic subgroup) and preferred name using the number and percentage of subjects for each dose cohort and overall. A subject reporting the same medication more than once within each ATC drug class will be counted only once when calculating the number and percentage of subjects who received that medication. Medications may appear under multiple ATC drug classes. The summary will be ordered alphabetically by ATC classification

and by preferred term in descending overall frequency within each ATC classification. For drugs with the same frequency, sorting will be performed alphabetically.

For the purposes of analysis, any medications with a start date prior to or on the first dosing date of study drug and continued to be taken after the first dosing date, or started after the first dosing date but prior to or on the last dosing date of study drug will be considered concomitant medications. Medications started and stopped on the same day as the first dosing date or the last dosing date of study drug will also be considered concomitant. Medications with a stop date prior to the date of first dosing date of study drug or a start date after the last dosing date of study drug will be excluded from the concomitant medication summary. If a partial stop date is entered, any medication with the month and year (if day is missing) or year (if day and month are missing) prior to the date of first study drug administration will be excluded from the concomitant medication summary. If a partial start date is entered, any medication with the month and year (if day is missing) or year (if day and month are missing) after the study drug stop date will be excluded from the concomitant medication summary. Medications with completely missing start and stop dates will be included in the concomitant medication summary, unless otherwise specified. Summaries will be based on the Safety Analysis Set. No formal statistical testing is planned.

All prior and concomitant medications (other than per-protocol study drugs) will be provided in a by-subject listing sorted by subject ID number and administration date in chronological order.

## **7.5.                   Electrocardiogram Results**

Electrocardiogram (ECG) analysis results are intended to identify meaningful changes in the QT interval. If potential abnormalities of interest are identified, further analyses may be conducted. Investigator assessment of ECG readings and ECG data will be provided for the Safety Analysis Set for each scheduled time point. No formal statistical testing is planned.

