Clinically significant, abnormal 12-lead safety electrocardiograms (ECGs) should be repeated. Subjects who have 2 consecutive ECGs showing a new absolute QTcF (Fridericia correction) duration > 500 ms, or a QTc > 60 ms over the corresponding baseline value must discontinue any medications that could prolong the QT interval (including oxaliplatin). Subject's concomitant medications should be reviewed to determine a potential etiology for the ECG changes. Appropriate intervention (ie, cardiology evaluation, telemetry monitoring, management of electrolyte abnormalities) in response to treatment-emergent QT interval prolongation should be initiated.

Should infusion reaction be considered a significant safety issue by the SRT, the SRT might decide to recommend premedication with an antihistamine and acetaminophen approximately 30 to 60 minutes before each dose of GS-1423 (eg, 25-50 mg diphenhydramine, 500-1000 mg acetaminophen or equivalent dose of antipyretic).). This regimen may be modified based on local treatment standards and guidelines, as appropriate.

Table 5-2 shows treatment guidelines for subjects who experience an infusion reaction associated with administration of GS-1423.

Subjects receiving GS-1423 should be monitored for infusion reactions. This includes the measurement of vital signs prior to each infusion commencing, at the end of each infusion, and for the first 2 cycles, 1 hour (\pm 15 minutes) after the end of the GS-1423 infusion. Thereafter, the final vital signs can be taken 30 minutes (-10/+20 minutes) after the end of the GS-1423 infusion. Subjects will remain in the clinic under close supervision for the duration of this monitoring period. Subjects with mild or moderate infusion reactions may receive GS-1423 with close monitoring. Premedication with an antipyretic or antihistamine for subsequent treatment administration may be considered. For severe infusion reactions, GS-1423 infusion must be discontinued, and appropriate medical therapy should be administered.

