8.7.4. Other Safety Evaluations

Similar general approaches to the AE and clinical laboratory data will be utilized to summarize other safety measures.

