### **3.8.2. Analysis Visit Windows**

The nominal visit as recorded on the CRF will be used when data are summarized by visit. Any data relating to unscheduled visits will not be assigned to a particular visit or time point. However, the following exceptions will be made:

- An unscheduled visit prior to the first dosing of study drug may be included in the calculation of the baseline value, if applicable.
- Unscheduled visits after the first dosing of study drug will be included in determining the maximum postbaseline toxicity grade.

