### **7.5.1.               Investigator Electrocardiogram Assessment**

A shift table of the investigators' assessment of ECG results at worst outcome during study compared with baseline values will be presented by dose cohort using the following categories: normal; abnormal, not clinically significant; abnormal, clinically significant; or missing. The number and percentage of subjects in each cross-classification group of the shift table will be presented. Subjects with a missing value at baseline or postbaseline will not be included in the denominator for percentage calculation. No formal statistical testing is planned.

A by-subject listing for ECG assessment results will be provided by subject ID number and visit in chronological order.

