### **7.5.2.               Corrected QT Intervals**

The QT interval (measured in millisecond [msec]) is a measure of the time between the start of the Q wave and the end of the T wave in the heart's electrical cycle. The QT interval represents electrical depolarization and repolarization of the ventricles. The QT interval is affected by heart rate, and a number of methods have been proposed to correct QT for heart rate.

Corrected QT (QTc) intervals will be derived using Fridericia's correction (QTcF) as follows:

$$QTcF = \frac{QT}{\sqrt[3]{RR}}$$

where QT is measured in msec; RR = 60/Heart Rate (beats per min [bpm]) and RR is measured in seconds

QTcF will be listed by-subject.

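### SAP 7.5 sets out to detect meaningful QT changes but plans only a by-subject QTcF listing: no change-from-baseline summary, no threshold counts and no rule for postbaseline triplicates

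*SAP*

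**What the plan says.** **Aim and outputs.** SAP 7.5 opens with "Electrocardiogram (ECG) analysis results are intended to identify meaningful changes in the QT interval". It then says "Investigator assessment of ECG readings and ECG data will be provided for the Safety Analysis Set for each scheduled time point" and adds "If potential abnormalities of interest are identified, further analyses may be conducted". SAP 7.5.1 gives one table: "ECG results at worst outcome during study compared with baseline values will be presented by dose cohort", using the investigator's categories (normal; abnormal, not clinically significant; abnormal, clinically significant; missing). It also gives a by-subject listing of those assessments. SAP 7.5.2 gives the Fridericia formula and then "QTcF will be listed by-subject".

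**Protocol.** Protocol 8.7 has on-treatment safety data summarized by dose level/cohort, with descriptive statistics for continuous measures. Protocol 8.7.4 adds "Similar general approaches to the AE and clinical laboratory data will be utilized to summarize other safety measures", and the laboratory approach in 8.7.3 summarizes both values and change from baseline. SAP 7.8 declares no deviation from the protocol's safety analyses.

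**Data collected.** Protocol 6.2.6 and SAP Appendix 1 (footnote f) schedule triplicate ECGs at Cycle 1 Day 1 predose, end of infusion, 24 h and 168 h. In Part A this applies to Cohorts 5-7 (20, 30 and 45 mg/kg). Footnote f also schedules an ECG 2 hours after dosing on Cycle 1 Day 1.

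**Unscheduled data.** SAP 3.8.2 does not assign unscheduled records to a visit. For postdose data it names one exception: "Unscheduled visits after the first dosing of study drug will be included in determining the maximum postbaseline toxicity grade".

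**The concern.** The section names a purpose, and no planned output serves it at cohort level. The shift table records a clinical judgement in categories. A modest drift in QTcF with dose need not move any subject to another category, so the table can look unremarkable while the interval lengthens. The listing holds the values, but the reader has to average triplicates, choose a baseline, subtract and compare cohorts by hand. The permitted further analyses depend on someone first noticing an abnormality, and no trigger is defined.

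Two neighbouring rules add to this. The baseline rule goes by date although there are postdose ECGs on the dosing date. It is also not stated whether unscheduled ECGs count in the worst-outcome shift table. That table is the one that delivers the Part A secondary endpoint in protocol 8.1.3, the percentage of subjects with a clinically significant abnormal 12-lead ECG.

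**Working it through.** The ECG section gives no sample size, error rate or other figure to reproduce, so the check compares passages, with short arithmetic where it applies.

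**1. Outputs against the aim.** SAP 7.5 specifies one summary table (investigator category) and two listings (assessments, QTcF). Summary tables containing a QTcF value or a QTcF change: 0. By contrast, SAP 7.3 gives body weight, BMI and each vital sign a by-cohort change and percentage change from baseline to the postbaseline maximum and minimum.

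**2. Against the protocol.** QTcF is a continuous safety measure, so the general sentence in protocol 8.7 covers it, and 8.7.4 points the same way. A listing is not a summary. The statement in SAP 7.8 is therefore not accurate for QTcF.

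**3. Triplicates.** Per subject in Cohorts 5-7: 4 time points × 3 tracings = 12 tracings. After averaging, these give 4 values and 4 − 1 = 3 changes from predose. SAP 3.8.3 averages multiple records for baseline only, and only if they share a time or have no time recorded. There is no postbaseline rule.

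**4. Baseline.** SAP 3.8.3 takes the last nonmissing value on or before the first dosing *date*. Protocol 8.4 uses the most recent value before treatment, and SAP 7.3 uses date/time for vital signs. SAP 7.5 has no such override. Write Qpre for the predose value, Q2h for the 2-hour value, Qt for a later value and d = Q2h − Qpre.
- Times recorded, rule read literally: baseline = Q2h. Computed change = Qt − Q2h = (Qt − Qpre) − d. A drug effect already present at 2 hours is subtracted out in full.
- Times not recorded, one predose and one 2-hour tracing: baseline = (Qpre + Q2h)/2. Computed change = (Qt − Qpre) − d/2.

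The same rule feeds the shift table, where a postdose assessment could be classed as baseline.

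**5. Thresholds.** Protocol 5.5.3 refers to QTcF > 500 ms, or QTc > 60 ms over baseline, on 2 consecutive ECGs. The SAP tabulates neither limit. The number of subjects with any such value and the number meeting the 2-consecutive condition are different counts and need separate rows.

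**6. Unscheduled ECGs.** Two readings are possible. SAP 3.8.2 governs by-visit summaries, and a worst-outcome table is not one, so unscheduled ECGs may enter. But the exception in 3.8.2 names another worst-value derivation, the maximum toxicity grade, and not ECG category, which suggests they may not. The choice affects the endpoint only for a subject whose *only* clinically significant ECG is unscheduled. Protocol 5.5.3 says "Clinically significant, abnormal 12-lead safety electrocardiograms (ECGs) should be repeated", but a repeat after a scheduled clinically significant ECG cannot lower that subject's worst outcome.

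**The case against.** The strongest defence is that this SAP serves a synoptic report of a study stopped after Part A, with 3 to 6 subjects per cohort plus optional additions. Individual QTcF values are listed, and at that scale a listing can be read. QTcF is not a named endpoint; the ECG endpoint is the percentage with a clinically significant abnormality, which the shift table delivers. Protocol 8.7.4 is generic, and further analyses are allowed.

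Much of this stands as a limit on the point. An individual outlier could be found in the listing, and the amount of output is partly the sponsor's choice. It does not answer the mismatch between the section's stated aim and its outputs. Nor does it answer protocol 8.7, which covers continuous safety data without relying on 8.7.4. A deliberate reduction would belong in SAP 7.8.

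A reader might infer more than the documents support:
- *That ECG reporting is confined to scheduled visits.* SAP 7.5 does not say only. The shift table is at worst outcome, and the listings carry no visit restriction.
- *That the triplicates are lost through the scheduled wording.* They are themselves scheduled, and nothing keeps their assessments out of the shift table. What they lack is an averaging rule and a numeric summary.
- *That a QT effect could not be seen at all.* The values are listed. The accurate statement is that no planned summary shows it.
- *That the mandated repeat ECGs cause an undercount.* Step 6 of the working shows they do so only if the triggering ECG was itself unscheduled.

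**Conclusion.** The point holds as a gap in planned analysis. SAP 7.5 does not plan the summary its own aim calls for, protocol 8.7 calls for one, and SAP 7.8 does not declare the difference. The baseline rule is a related defect: read literally it can take a postdose tracing as baseline and understate QTcF change by up to the full 2-hour effect. This assumes the date-based wording is applied as written; a programmer who reads baseline as predose would avoid it.

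The documents support no estimate of bias or of a miscounted rate. The size is one absent by-cohort table, covering 4 averaged values and 3 changes from predose per subject at the triplicate time points in Cohorts 5-7, plus the single ECGs at other scheduled time points in all cohorts. The handling of unscheduled ECGs is an ambiguity to settle. It is not evidence that records are dropped.

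**What to change.** 1. **SAP 7.5.2:** add a by-cohort table of QTcF and change from the Cycle 1 Day 1 predose value at each scheduled time point, using the mean of each triplicate where taken. Add counts of subjects with any QTcF > 500 ms or any increase > 60 ms and, in a separate row, subjects meeting the 2-consecutive-ECG condition in protocol 5.5.3. These serve as reporting categories only and change no clinical rule.
2. **SAP 7.5 or 3.8.3:** define the ECG baseline as predose by date and time, and state the averaging rule for postbaseline triplicates.
3. **SAP 3.8.2 (secondary):** state that unscheduled postdose ECGs enter the worst-outcome shift table, and that unscheduled vital signs enter the maxima and minima in SAP 7.3.
4. If the sponsor prefers to keep a listing only, SAP 7.8 should declare it as a reduction from protocol 8.7. That settles the disclosure but leaves the stated aim unmet.

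The cost is one extra table in a synoptic report and a few sentences. No new data are needed: the ECGs are already scheduled, and protocol 6.5 has unscheduled data captured in the eCRF.
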